8.2.1.3. Assessment of Adverse Events

Each AE will be assessed by the Principal Investigator as per the categories discussed in the following sections.

8.2.1.3.1. Intensity

The Principal Investigator will assess all AEs for severity in accordance with the following standard ratings.

- Mild (Grade 1): Ordinarily transient symptoms, does not influence performance of subject’s daily activities. Treatment is not ordinarily indicated.
- Moderate (Grade 2): Marked symptoms, sufficient to make the subject uncomfortable. Moderate influence on performance of subject’s daily activities. Treatment may be necessary.
- Severe (Grade 3): Symptoms cause considerable discomfort. Substantial influence on subject’s daily activities. May be unable to continue in the study and treatment may be necessary.
- Potentially Life Threatening (Grade 4): Symptoms require emergency room (ER) visit or hospitalization.

When changes in the intensity of an AE occur more frequently than once a day, the maximum intensity for the event should be noted for that day. Any change in severity of signs and symptoms

over a number of days will be captured by recording a new AE, with the amended severity grade, and the date (and time, if known) of the change.

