	
2 years prior to enrollment (Note: one unit = 12 ounces of beer, 4 ounces of wine or 1 ounce of spirits)
 
 16. Smoking any amount within 3 months prior to enrollment 17. Excessive consumption of tea, coffee, and/or caffeinated beverages (more than 8 cups, 250 mL for each cup) every day within 3 months prior to enrollment 18. Symptomatic viral, bacterial (including upper respiratory infection), or fungal (non-cutaneous) infection within 1 week prior to enrollment 19. History of human immunodeficiency virus antibody, hepatitis C antibody or hepatitis B virus surface antigen 20. A history of psychiatric and psychological condition that, in the judgment of the investigator, may interfere with the planned treatment and follow-up, affect subject compliance or place the subject at high risk from treatment-related complications 21. Poor venous access or inability to tolerate venipuncture 22. Any condition or active drug treatment that the investigator or primary physician believes may not be appropriate for participating in the study
Duration of Study	
The duration of participation for each subject will be approximately 84 days (12 weeks)
 
 • Screening Period: Up to 28 days (4 weeks) • Run-in Visit: Up to 14 days (2 weeks) • Treatment Period: 28 days on ARD-101 (4 weeks) • Follow-up Period: 14 days (2 weeks). The End of Study (EOS) Visit will occur within 14 days after receiving the dose of ARD-101
Pharmacodynamic Evaluation	
All subjects will be required to provide blood samples at defined time points and at the end of treatment visit. These blood samples will be used to explore the parameters described in the endpoint setting. The Control of Eating Questionnaire (CoEQ) will be administered at the timepoints indicated in Table 1.

Safety Evaluations	
Adverse events (AE) will be collected from the time of informed consent until 14 days after the last administration of study drug. Safety laboratory assessments, including CBC, chemistries, coagulation tests, urinalysis, and thyroid function, along with ECGs, , and vital signs will be obtained. All concomitant medications will be recorded. All adverse events will be followed to resolution or stabilization. Only TEAE will be summarized.

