Grade 1	1 (16.7%) [2]	1 (25.0%) [4]	1 (20.0%) [2]	2 (50.0%) [5]	5 (26.3%) [13]
Grade 2	---	---	2 (40.0%) [2]	1 (25.0%) [1]	3 (15.8%) [3]
Grade 3	---	---	---	---	---
Grade 4	---	---	---	---	---

BID = twice daily; nE = number of adverse events; nS = number of subjects with an adverse event; N = number of subjects; % = percentage of subjects with an adverse event (nS/N×100)

Severity grades: 1 = mild; 2 = moderate; 3 = severe; 4 = potentially life-threatening

Adverse events were assigned severity grade using the Toxicity Grading Scale for Healthy Adult and Adolescent Volunteers Enrolled in Preventive Vaccine Clinical Trials Version September 2007.

A treatment-

emergent adverse event (TEAE) was defined as an adverse event that started during or after the first dose, or started prior to the first dose and increased in severity after the first dose.

A treatment-related TEAE was defined as a TEAE with a relationship of related to the study treatment, as determined by the investigator.

Where a subject experienced multiple TEAEs with the same preferred term for the same treatment, this was counted as 1 TEAE for that treatment under the maximum severity recorded.

Table 7 Summary of Treatment-related Treatment-emergent Adverse Events by System Organ Class and Preferred Term - MAD Part

System Organ Class Preferred Term	Placebo (BID) (N = 6) nS (%)	40 mg ARD-101 (BID) (N = 4) nS (%)	100 mg ARD-101 (BID) (N = 5) nS (%)	240 mg ARD-101 (BID) (N = 4) nS (%)	Overall (N = 19) nS (%)
Overall	1 (16.7%)	1 (25.0%)	2 (40.0%)	3 (75.0%)	7 (36.8%)
Gastrointestinal disorders	1 (16.7%)	1 (25.0%)	1 (20.0%)	1 (25.0%)	4 (21.1%)
Diarrhoea	---	---	1 (20.0%)	1 (25.0%)	2 (10.5%)
Dyspepsia	---	1 (25.0%)	---	1 (25.0%)	2 (10.5%)
Nausea	---	1 (25.0%)	1 (20.0%)	---	2 (10.5%)
Abdominal distension	---	1 (25.0%)	---	---	1 (5.3%)
Abdominal pain	---	---	1 (20.0%)	---	1 (5.3%)
Flatulence	1 (16.7%)	---	---	---	1 (5.3%)
Nervous system disorders	1 (16.7%)	1 (25.0%)	---	2 (50.0%)	4 (21.1%)
Headache	1 (16.7%)	1 (25.0%)	---	---	2 (10.5%)
Dizziness	---	---	---	1 (25.0%)	1 (5.3%)
Dysgeusia	---	---	---	1 (25.0%)	1 (5.3%)
Skin and subcutaneous tissue disorders	---	---	1 (20.0%)	1 (25.0%)	2 (10.5%)
Urticaria	---	---	1 (20.0%)	1 (25.0%)	2 (10.5%)
Cardiac disorders	---	---	---	1 (25.0%)	1 (5.3%)
Palpitations	---	---	---	1 (25.0%)	1 (5.3%)

BID = twice daily; nS = number of subjects with an adverse event; N = number of subjects; % = percentage of subjects with an adverse event (nS/N×100)

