9.7.1. Adverse Events

All AEs will be listed. The number and percent of subjects experiencing an event will be tabulated for each SOC and PT. The AEs will also be tabulated according to intensity and causality. A TEAE is defined as an AE with a start date on or after the first dose of study drug, or that worsened following first administration of study drug. For purposes of data analysis, the end of the TEAE period will be the last time point when a subject was evaluated for AEs.

The AEs (TEAEs) will be tabulated according to intensity and causality, as applicable.

Non-TEAEs will be listed, as applicable.

Serious AEs will be listed separately.

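### Read together, the AE severity-change rule and the TEAE start-date rule can count a pre-dose event that only improves after dosing as treatment-emergent.

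*Combined protocol and SAP*

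**What the plan says.** **Recording.** Section 8.2.1.3.1 applies to "Any change in severity of signs and symptoms", with no limit on direction. A change that spans days "will be captured by recording a new AE, with the amended severity grade, and the date" on which it happened. The one exception is within-day fluctuation, where only the daily peak is kept: "When changes in the intensity of an AE occur more frequently than once a day, the maximum intensity for the event should be noted".

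**Classification.** Section 9.7.1 states: "A TEAE is defined as an AE with a start date on or after the first dose of study drug", and adds "or that worsened following first administration of study drug". It does not say how a follow-on record relates to the record it came from.

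**Collection and use.** AEs are collected from signature of the consent form (8.2.1 and 8.2.1.2), and Table 1 opens screening at Day -42. Section 8.2.1.1.1 confirms that untoward events during screening are AEs; illness present before study entry is not an AE unless it worsens during treatment. TEAE incidence is a secondary endpoint (3.2). Section 9.7.1 tabulates the number and percentage of subjects with an event by system organ class and preferred term, and also tabulates by intensity and causality.

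**The concern.** The two sections were not reconciled. The second limb of the TEAE definition shows the intent: an event already present at first dose should count only if it gets worse. The recording rule turns any multi-day change into a fresh AE, so the first limb picks up the new record on its date alone, whichever way the grade moved. For a recorded AE, worsening already creates a post-dose record, so the second limb adds almost nothing and the first limb admits improvement too.

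At stake is a secondary endpoint in a single-arm study of 25 to 30 subjects. With no control group in which the same artefact would occur, a false TEAE goes straight into the reported incidence.

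**Working it through.** The plan states no figure to reproduce; the sample size is declared not to be power based (9.9). The check is to apply the two rules as written, then size the result.

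**Step 1. Apply the rules to example courses.** Each change to a different nonzero grade makes a new record dated at the change (8.2.1.3.1). A record dated Day 1 or later is a TEAE (9.7.1, first limb). The comparison rule counts only a new onset on or after first dose, or a grade above the last pre-dose grade.

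| Course of one AE | Records | TEAE as written | TEAE by onset or worsening |
|---|---|---|---|
| Grade 2 on Day -10, Grade 1 on Day 3 | 2 | yes | no |
| Grade 3 on Day -5, Grade 2 on Day 2, Grade 1 on Day 5 | 3 | yes | no |
| Grade 1 on Day -10, resolved on Day 3 | 1 | no | no |
| Grade 2 on Day -10, unchanged | 1 | no | no |
| Grade 1 on Day -10, Grade 2 on Day 3 | 2 | yes | yes |
| New Grade 1 on Day 4 | 1 | yes | yes |

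The rules disagree only in the first two rows. The event must start after consent, be at Grade 2 or higher at first dose, and step down to a lower nonzero grade. A Grade 1 event that improves simply resolves and makes no new record.

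**Step 2. Effect of one case.** Planned enrolment is 30 (4.1); the sample-size section says 25 (9.9).

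- 1/30 = 3.3 percentage points; 1/25 = 4.0 percentage points.
- For overall TEAE incidence, this applies only if the subject has no other TEAE.
- For a preferred-term percentage, it applies only if the subject has no other TEAE of that term.

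**Step 3. Expected effect under assumed rates.** Let q be the share of subjects with such a step-down event and p the true TEAE incidence, and assume the two are independent. The expected rise in overall incidence is q × (1 − p). The documents give no value for q. For p, an illustrative value comes from Table 6: ARD-101 subjects with any TEAE in the multiple-dose part were 1 + 3 + 3 = 7 of 4 + 5 + 4 = 13, so p = 53.8% and 1 − p = 6/13.

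| q (assumed) | Rise at p = 53.8% |
|---|---|
| 1/30 | 1/30 × 6/13 = 1.5 points |
| 5% | 0.05 × 6/13 = 2.3 points |
| 10% | 0.10 × 6/13 = 4.6 points |
| 20% | 0.20 × 6/13 = 9.2 points |

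At q = 10%, the rise is 0.10 × 0.75 = 7.5 points if p = 25%, and 0.10 × 0.25 = 2.5 points if p = 75%.

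**Step 4. Look for a passage that removes the problem.** The carve-out in 8.2.1.1.1 covers illness before study entry, not AEs that arise between consent and Day 1. Section 8.2.1.2 asks for an onset date for each AE, but the only date 8.2.1.3.1 gives the new record is that of the change. Section 9.8 defers only exploratory analyses to the SAP. None of these resolves it.

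**The case against.** **Ambiguity.** Section 8.2.1.3.1 asks for the date of the change and does not call it a start date, and the second limb of 9.7.1 signals that only worsening should count. A careful programmer might reach the intended result. This stands in part and is why confidence is moderate. Still, a new AE record dated at the change has no other onset date to use.

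**Rarity.** Criterion 8 in 5.2 requires no clinically significant abnormal findings at screening, and criterion 18 in 5.3 excludes recent symptomatic infection. A reader might infer that the run-in procedures (meal test, intravenous line, glucose sensor) would supply many cases, but nothing in the documents suggests that they cause Grade 2 or higher events lasting past Day 1. This objection stands.

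**Consequence.** The analysis is descriptive, the error overcounts rather than hides harm, and all AEs are listed, so a case could be found. This also stands and keeps the severity low.

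**Stronger readings that the documents do not support.**

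- A reader might infer that split records inflate the endpoint generally. A post-dose event going Grade 1 to 2 to 1 does make three records, but it is a true TEAE and 9.7.1 counts subjects, so incidence is unchanged. Only the intensity table is affected, because it has no maximum-severity rule.
- A reader might think that the first-in-human convention would cure this. Under Table 6, a repeat of the same term "this was counted as 1 TEAE for that treatment under the maximum severity recorded". That footnote belongs to the earlier study, and collapsing would not remove a step-down record that is the only one of its term.
- A reader might see a contradiction with the synopsis, which says "Only TEAE will be summarized". The opening of 9.7.1 is loosely worded, but the section goes on to tabulate TEAEs and list non-TEAEs, which largely agrees.

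**Conclusion.** The point holds in a narrow form. The two rules as written misclassify an AE that arose between consent and Day 1, was still at Grade 2 or higher at first dose, and then fell to a lower nonzero grade. That is an error on a secondary endpoint and not merely missing detail, because both rules are stated and together they contradict the worsening test in the same definition.

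The size is one subject at a time, under the conditions in Step 2. It would be wrong to infer that every severity change, or every affected subject, moves the endpoint: within-day changes are recorded only at the daily maximum, and a subject with another TEAE is already counted. The expected effects in Step 3 rest on assumed frequencies and on independence of the two events. Label: wrong as written; low severity, moderate confidence.

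**What to change.** In 9.7.1, add:

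1. For TEAE classification, a severity-change record made under 8.2.1.3.1 keeps the onset date of the original event.
2. An event with onset before first dose is treatment-emergent only if its grade after first dose exceeds its last pre-dose grade.
3. In the intensity table, each subject counts once per preferred term at the maximum post-dose grade, so that split records do not place one event in several grades.

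The cost is three sentences of analysis text. Visits, procedures and the recording rule need not change. Programmers must be able to tell which records belong to one event; a field linking a record to its original AE would make that explicit but is optional.

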8.2.1.3.2. Causality

The Principal Investigator will assess the causality/relationship between the study medication and the AE. The Principal Investigator is responsible for assessing the relationship to study medication using clinical judgment and the following considerations:

- No: Evidence exists that the AE has an etiology other than the study drug. For SAEs, an alternative causality must be provided (e.g., pre-existing condition, concomitant medication)
- Yes: There is reasonable possibility that the event may have been caused by the study medication.

8.2.1.4. Reporting of Serious Adverse Events

The Principal Investigator will review each SAE and evaluate the intensity and the causal relationship of the event to study drug. All SAEs will be recorded from signing of the ICF until the EOS Visit. Serious AEs occurring after the EOS Visit and coming to the attention of the Principal Investigator must be reported only if there is (in the opinion of the Principal Investigator) reasonable causal relationship with the study drug.

The Principal Investigator is responsible for providing notification to Sponsor of any SAE, whether deemed study medication-related or not, that a subject experiences during their participation in study within 24 h of becoming aware of the event.

Initial reports of SAEs must be followed later with detailed descriptions, including clear photocopies of other documents as necessary (e.g., hospital reports, consultant reports, autopsy reports), with the subject's personal identifiers removed.

Information on SUSARs will be collected and reported to the regulatory authority and the IEC as required per guidelines.

If the SUSAR is fatal or life-threatening, associated with the use of the study medication, and unexpected, the regulatory authority and the IEC will be notified per guidelines after being made aware of the case. Additional follow-up (cause of death, autopsy report, hospital report) information should be reported per guidelines. SUSARs which are not fatal and not life-threatening are to be reported per guidelines.

The Sponsor will notify the Investigators of relevant information about SUSARs that could adversely affect the safety of subjects in a timely fashion. Follow-up information may be submitted if necessary. The Sponsor will also provide annual safety reports for submission to the regulatory authority and the IEC responsible for the clinical study. These updates will include information on SUSARs and other relevant safety findings.

8.2.1.5. Follow-up of Adverse Events

All AEs experienced by a subject, irrespective of the suspected causality, will be monitored until the event has resolved, until any abnormal laboratory values have returned to baseline or stabilized at a level acceptable to the Principal Investigator and Medical Monitor, until there is a satisfactory explanation for the changes observed or until the subject is lost to follow-up.

8.2.1.6. Pregnancy

The Sponsor has a responsibility to monitor the outcome of all pregnancies reported during the clinical study.

Pregnancy alone is not regarded as an AE unless there is a suspicion that the study drug may have interfered with the effectiveness of a contraceptive medication. Elective abortions without complications should not be regarded as AEs, unless they were therapeutic abortions (see below). Hospitalization for normal delivery of a healthy newborn should not be considered an SAE.

Each pregnancy must be reported by the Principal Investigator to the Sponsor within **2 days** after becoming aware of the pregnancy. The Principal Investigator must follow-up and document the course and the outcome of all pregnancies even if the subject was withdrawn from the clinical study or if the clinical study has finished.

All outcomes of pregnancy must be reported by the Principal Investigator to the Sponsor on the pregnancy outcome report form within **2 days** after he/she has gained knowledge of the normal delivery or elective abortion.

Any SAE that occurs during pregnancy must be recorded on the SAE Report Form (e.g., maternal serious complications, therapeutic abortion, ectopic pregnancy, stillbirth, neonatal death, congenital anomaly, birth defect) and reported within 24 h in accordance with the procedure for reporting SAEs.

8.2.2. Clinical Laboratory Assessments

Samples for clinical laboratory assessments will be collected at the time points detailed in the Schedule of Assessments (Table 1). Samples will be collected in appropriate tubes and handled according to standard procedures of the applicable laboratory.

Any value outside the normal range will be flagged for the attention of the Principal Investigator or designee at the site. The Principal Investigator or designee will indicate whether the value is of clinical significance. Additional testing during the study may be done if medically indicated. If a clinically significant abnormality is found in the samples taken after dosing, during the study, and/or at the EOS Visit, it should be recorded as an AE and the subject will be followed until the test(s) has (have) normalized or stabilized, at the discretion of the Principal Investigator.

8.2.3. Vital Signs

Vital signs will be assessed at the time points detailed in the Schedule of Assessments Table 1. The following vital signs will be measured:

- Blood pressure (systolic and diastolic [mmHg])
- Pulse (bpm)
- Body temperature (°C)
- Respiratory rate (breaths per minute)

8.2.4. Standard 12-lead Electrocardiograms

Standard safety 12-lead ECGs will be performed at the time points detailed in the Schedule of Assessments (Table 1).

The ECG will include all 12 standard leads.

All ECGs must be evaluated by a qualified physician for the presence of abnormalities. If a clinically significant abnormality is found, it should be recorded as an AE and the subject will be followed until the test(s) has (have) normalized or stabilized, at the discretion of the Principal Investigator.

8.2.5. Bioimpedance

Body composition will be assessed via scale measuring bioimpedance at the time points detailed in the Schedule of Assessments (Table 1).

8.2.6. MRI PDFF and Full Body Composition Scan

In order to better assess overall body composition including quantification of lean body mass, liver fat content and other related parameters, MRI scan will be performed at the time points detailed at the time points detailed in the Schedule of Assessments (Table 1).

8.2.7. Mixed Meal Tolerance Test (MMTT)

The MMTT permits measurement of intestinal (incretin secretion), β -cell (insulin secretion), hepatic (insulin extraction), muscle, and adipose tissue responses to ingesting calories. The mixed meal, containing glucose, fat and protein (2x Ensure 8 oz. for a total of 16 oz., 66 grams carbohydrate (CHO), 440 calories), is more physiologic than the glucose only challenge in an oral glucose tolerance test (OGTT). The MMTT will be performed at the time points detailed in the Schedule of Assessments (Table 1) and as described in the Appendix. (Table 1).

8.2.8. Indirect Calorimetry

Continuous indirect calorimetry using a commercial instrument (Vmax Encore VS 29N, CareFusion, Yorba Linda, CA, USA) will be performed during basal and postprandial periods on the days when the MMTT are performed.

At -80 and 195 minutes during the MMTT, the canopy will be placed over the subject's head to collect data from 10 continuous minutes at steady-state (no longer than 30 minutes) during each interval for determination of the substrate oxidation rates at basal condition, and during the MMTT as outlined in the Schedule of Assessments (Table 1).

8.2.9. Physical Examinations

Physical examinations will be performed at the time points detailed in the Schedule of Assessments (Table 1).

Full physical examination:

An assessment of general appearance and a review of systems (dermatologic, head, eyes, ears, nose, mouth/throat/neck, thyroid, lymph nodes, respiratory, cardiovascular, gastrointestinal, extremities, musculoskeletal, neurologic and psychiatric systems).

Brief physical examination:

An assessment of the general appearance, skin, cardiovascular system, respiratory system and abdomen.

The brief physical examination may be extended to a full physical examination if considered necessary by the Principal Investigator. Other evaluations may be performed as deemed necessary by the Principal Investigator.

8.2.10. Continuous Glucose Monitoring

Assessments will be performed at the time points detailed in the Schedule of Assessments (Table 1).

Glucose levels will be monitored using the Continuous Glucose Monitoring (CGM) device. The CGM device will be used to track blood sugar levels day and night, and it will collect readings automatically every 5 minutes. The CGM sensor is a round disk with the circumference equal to that of a quarter, with the thickness of 2 quarters. It has a small filament that is inserted subcutaneously via a small needle that is then retracted and removed, leaving just the filament. The CGM sensor adheres to the skin leaving the filament in place for 14 days and stores the recorded glucose readings until downloaded by a study team member.

During the Run-in Period, the CGM sensor will be applied to the subject and they will be required to wear it for a minimum duration of two weeks prior to Treatment Period Day 1. Data from the CGM will be downloaded and a report will be generated using the software provided by the device. The report outlines typical measures of glycemic control: mean glucose, standard deviation, time in range and daily patterns. In addition, a raw data file is available with each time point of collection and glucose reading.”

